 - i. Levels of engagement (i.e. percent of chapters completed), ratings of satisfaction, and dropout rates from the intervention
 - ii. Levels of engagement in the program as a function of individual characteristics and risk profile
 - iii. Levels of engagement as a moderator of within person change in outcomes.
 - iv. Association between change in modifiable risk factors and change in cognition
- D.** To develop a successful comprehensive national recruitment plan to fully enroll the PTC with engagement stakeholder groups including participants, citizen advisors, and community partners

3 Power and Sample Size Determination

Sample size/power calculation was done based on effect size for one-group pre-/post-design. According to Becker, the effect size ¹ for such a design should be defined as, assuming the standard deviation (SD) at pre- and post-test are equal,

$$ES = \frac{\text{mean change}}{\text{SD baseline}} = \frac{\text{mean change}}{\text{SD change} / \sqrt{2(1 - r)}}$$

where r is correlation between pre- and post-scores. Note that

$$\text{var}(\text{mean change}) = 2\text{var}(\text{baseline})(1 - r)$$

Sample size can then be determined based on the following test statistic

$$T = \frac{\text{mean change}}{\text{SD change}/\sqrt{n}} = \frac{\text{ES}}{\sqrt{2(1-r)/n}}$$

i.e., the corresponding sample size formula for 80% power at 5% significance level to detect ES is given by

$$n = \frac{(1.96 + 0.84)^2}{(\text{mean change}/\text{SD change})^2} + 2 = \frac{(1.96 + 0.84)^2}{\text{ES}^2/[2(1-r)]} + 2$$

Note that plus 2 ($\approx 2 \times 1.96^2$) is to approximate Z-test with sample size for t-test².

Therefore, the sample sizes for detecting small and moderate magnitudes of ES³ at 2-sided 5% significance level with 80% power are given below for values of correlation r

ES	r	n
0.2 (small)	0.2	316
	0.3	277
	0.4	238
	0.5	198
0.5 (medium)	0.2	53
	0.3	46
	0.4	40
	0.5	34

4 Samples of Interest

- a. **Enrolled Sample:** Includes all participants who consented to screening.
- b. **Intention To Treat (ITT) Sample:** Includes all participants who (1) meet screening criteria (2) and completed at least 1 assessment at baseline.
- c. **Modified Intention to Treat (mITT) Sample:** Includes all eligible participants who (1) have completed at least one assessment for the outcome of interest and (2) registered for BHP.

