- d. **Completers Sample (CS):** Includes all eligible participants who have completed the baseline and 12-month assessment for the primary outcome.

5 Enrollment and Participant Flow

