8.1 Overview of Statistical Approach

In our one-group pretest-posttest design the major interest is within-person change in the primary and secondary outcomes over time (response variables) in the presence of one or more explanatory variables that are categorical or continuous. The data will be analyzed using a mixed model for repeated measures approach (MMRM)⁴. Example R code using the 'nlme' and 'emmeans' statistical packages is given by:

```
mdl = temp_data |>
  gls(Score ~ factor(Time) + Age + Sex + Education,
      na.action = na.omit, data = ,
      correlation = nlme::corSymm(form=~Time |Site/Identifiers),
      weights = varIdent(form = ~1|Time))
emmeans(mdl, ~Time, contr = "pairwise")
```

This approach will treat sites and participants as random effects, while observational time and their characteristics such as sex, age and education as fixed effects. Potential effect modifications will be examined using this MMRM approach with variable selection based on Akaike/Bayesian information criterion. The MMRM approach effectively handles missing data, with the assumption that data are missing at random. In this approach, information on missing observations is recovered from the observed outcomes via the within-patient correlation structure. In contrast to the flawed method of last observation carried forward⁵, which uses only one data point, a MMRM analysis uses all the available data to compensate for the data missing on a particular patient.

However, because there is missing data at baseline for certain outcome measures—including the primary outcome because of a technical issue in the measure administration—the MMRM approach on the observed data will not provide inferences on the intention-to-treat (ITT) sample. This is because the MMRM excludes all individuals without at least one measurement of the outcome of interest. To address this issue, multiple imputation of missing data will be undertaken prior to fitting the MMRMs. Forty data sets will be imputed by chained equations (that is, fully conditional specification) using the R package 'mice'⁶ using predictive mean matching (continuous variables), polytomous logistic regression (unordered factors), and logistic

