regression (binary factors) following 40 iterations of a Gibbs sampler for each imputed data set. The imputation model will include all time-varying primary, secondary and exploratory outcomes, as well as age, sex, education, racial/cultural background, cognitive diagnostic group, and study site. The sequence of missing data imputation will be ordered from the variable with the smallest percent missing to the variable with the most percent missing. A seed will be specified so that the imputation solution is reproducible.

The quality of the imputed values will be assured by evaluating the distribution of imputed values and examination of trace plots for proper mixing and absence of spikes in the iterations. Subsequent analyses will be conducted on each of the imputed data sets with estimates then being pooled using Rubin's rule ⁷ and degrees of freedom calculated using the Barnard-Rubin adjustment ⁸.

The primary analysis sample will be the ITT sample, i.e., participants with at least one outcome measure will be included in the analyses. As noted above, this will be achieved by fitting MMRMs on the multiply imputed data. As sensitivity analyses, the MMRMs will be fit to the observed data from the mITT and Completers samples. Sex-stratification will be used in analyses as appropriate.

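### If any ITT members never registered for BHPro, their ADKS is imputed entirely from registered users under MAR, and neither planned sensitivity analysis can test that

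*SAP*

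**What the plan says.** **Samples.** SAP 4 defines ITT as: "Includes all participants who (1) meet screening criteria (2) and completed at least 1 assessment at baseline". BHPro registration is not required. The mITT sample needs people who "have completed at least one assessment for the outcome of interest and (2) registered for BHP". The Completers sample is: "Includes all eligible participants who have completed the baseline and 12-month assessment for the primary outcome".

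**Primary analysis.** SAP 8.1 says: "The primary analysis sample will be the ITT sample, i.e., participants with at least one outcome measure will be included in the analyses". It gives the reason for imputing: "the MMRM excludes all individuals without at least one measurement of the outcome of interest". It adds that the primary outcome has missing baseline values "because of a technical issue in the measure administration". Imputation is by chained equations, with predictive mean matching for continuous variables. On predictors, "The imputation model will include all time-varying primary, secondary and exploratory outcomes", together with demographics, diagnostic group and site. No registration indicator is named.

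**Sensitivity.** "As sensitivity analyses, the MMRMs will be fit to the observed data from the mITT and Completers samples".

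**Where the ADKS is collected.** Protocol 8.3.3, 10.3 and Appendix 2 (footnote 13) place it inside the BHPro website. Protocol 8.1.4 puts BHPro registration after the baseline video visit and the LORIS questionnaires, within about two weeks.

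**The concern.** A person can enter ITT through the baseline test battery or a mood questionnaire and never register for the program. Such a person has no ADKS at any visit. Imputation under MAR then fills all three ADKS scores from people who did register, and so tends to credit a non-user with a user's gain. MAR is hard to defend for people who never received the program. They are also exactly the people whom both sensitivity analyses leave out. At stake is the size of the reported ITT change in dementia literacy.

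**Working it through.** **1. Whom imputation adds.** A mixed model on observed data keeps anyone with at least one ADKS. Imputation therefore adds only people with none, and these can be of two kinds:
- registered people who lost the baseline ADKS and left before Month 6, for whom MAR is plausible;
- people who never registered. That they have no ADKS is an inference from where the scale is collected.

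**2. Whether a planned check covers the second kind.** mITT requires registration. Completers does not mention registration, but it needs an observed ADKS at baseline and Month 12, which a non-registrant cannot have. Neither sample includes them.

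**3. Scale.** The plan's sample-size formula is n = (1.96 + 0.84)² × 2(1−r)/ES² + 2. At ES = 0.2 and r = 0.4 this is 7.84 × 1.2/0.04 + 2 = 237.2, rounded up to 238 as stated. All eight tabled values reproduce. They are not in dispute; the planned effect sizes of 0.2 and 0.5 baseline SD are used below only for scale.

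**4. Formula.** Let f be the share of ITT never registered, d the users' gain, g the gain imputed to non-registrants, and 0 their true gain.
- ITT estimate: (1−f)d + fg, which equals d when g = d.
- All-ITT mean: (1−f)d.
- Overstatement when g = d: fd in SD units, or f/(1−f) relative to the all-ITT mean.

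Both f and the zero true gain are assumptions.

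| f | People of 350 | f/(1−f) | f × 0.2 SD | f × 0.5 SD | Simulated, d = 0.2 | Simulated, d = 0.5 |
|---|---|---|---|---|---|---|
| 2% | 7 | 0.02/0.98 = 2.0% | 0.004 | 0.010 | 0.005 | 0.010 |
| 5% | about 18 | 0.05/0.95 = 5.3% | 0.010 | 0.025 | 0.011 | 0.026 |
| 10% | 35 | 0.10/0.90 = 11.1% | 0.020 | 0.050 | 0.021 | 0.052 |

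The simulated columns give the planned ITT estimate minus the no-gain estimate, with chapter completion left out of the imputation model. Settings: chained predictive mean matching, 5 donors, n = 350, 10 imputations (the SAP plans 40), 200 replicates. Assumed: visit correlation 0.5, 10% missing baseline ADKS, 25% missing Month 12 (half of these also missing Month 6). The estimates share a sampling offset of +0.007 to +0.010 SD, so the difference is the figure to read.

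**5. When g is close to d.** At f = 10%, the gain imputed to non-registrants was:

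| Chapter completion in the imputation model | d = 0.2 | d = 0.5 |
|---|---|---|
| Included, missing for non-registrants | 0.201 to 0.210 | 0.506 to 0.510 |
| Coded 0, gain unrelated to chapters | 0.215 | 0.509 |
| Coded 0, gain proportional to chapters | 0.020 | 0.019 |

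Monte Carlo SE is 0.006 in the first row and 0.014 in the others. In the last row at d = 0.2 the overstatement falls to about 0.10 × 0.020 = 0.002 SD. A separate, smaller simulation (r = 0.4, d = 0.2, 3 imputations, 60 replicates, f = 10% and 20%) showed the same pattern: 0.17 to 0.24 with chapters left out, 0.17 to 0.19 with chapters missing, 0.21 to 0.22 with chapters coded 0 and gain unrelated, and about 0.04 with chapters coded 0 and gain proportional. Its ITT estimates (Monte Carlo SE about 0.01) are too noisy to show a 0.02 SD effect on their own.

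**6. Null case.** With d = 0 and f = 10%, over 1000 replicates, the mean ITT change was 0.001 and rejection was 6.2% (Monte Carlo SE 0.7), consistent with 5%.

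**7. What the planned tables would reveal.** ITT N minus mITT N caps the number never registered but mixes both kinds in step 1. If that difference is 10% of ITT and 0%, 25%, 50% or 100% of it never registered, then f is 0%, 2.5%, 5% or 10% and the overstatement is 0%, 2.6%, 5.3% or 11.1%.

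**The case against.** **The group may be empty.** This stands. The only cause the SAP gives for missing baseline ADKS is a technical fault, not failure to register. Registration is explained at the baseline visit, and technical ability is an inclusion criterion. A reader might infer that the primary sample is known to contain non-users; the documents do not say so. They do treat registration as a separate step: mITT lists it as a condition, and Protocol 8.1.9 frames its discontinuation follow-up around people who completed it.

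**The existing plan may already handle it.** Partly right. Percentage of chapters completed is a secondary outcome tracked over time, so the predictor list can be read to include it, and 0 is a natural value for someone who opened none. But the SAP neither names it there nor states its coding, and it helps only if gain depends on chapters.

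**The users' gain is the target.** The primary aim in SAP 2 concerns change after participation in BHPro, and the ITT estimate stays close to the users' gain. It is too high only against an average over all ITT members that counts non-users as zero, and the SAP does not spell out that target. This stands as a limit on the point. An ITT label nevertheless invites that reading.

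**The wording of the ITT sample may exclude them.** If the phrase in SAP 8.1 meant at least one ADKS, non-registrants would drop out, but imputation would then add nobody, contrary to its stated purpose. It may simply mean any study outcome, which broadly agrees with SAP 4.

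**The extra analysis is nearly a multiplication by (1−f).** True: 0.9 × 0.209 = 0.188, as simulated. But f must first be reported. SAP 6 plans reasons for not moving forward at each stage; whether registration is one of its stages cannot be judged from the text available.

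**Conclusion.** The point holds as a conditional one. If any ITT members never registered, the primary analysis imputes their ADKS wholly from registered people, and no planned analysis tests the MAR assumption for them. They receive roughly the users' gain unless chapter completion is in the model, coded 0 for them, and related to gain. Measured against an all-ITT mean with zero gain for non-users, the overstatement is 2.0%, 5.3% and 11.1% at f = 2%, 5% and 10%. That is at most 0.020 SD for a users' gain of 0.2 SD and 0.050 SD for 0.5 SD over that range. The share f is assumed and may be zero, and zero gain cannot be checked from the data.

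A reader might infer that the trial could declare an effect that is not there, or that the primary analysis is invalid. Neither follows: if users gain nothing, there is no gain to pass on, and the estimate otherwise remains close to the gain among users. This is a cheap improvement.

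**What to change.** - Keep the MAR-imputed ITT analysis as primary.
- If any ITT members never registered, add one sensitivity analysis of the same model that sets their post-baseline ADKS equal to their imputed baseline (no gain), and report it beside the primary result. Its SE is slightly too small because zero gain is treated as known (simulated 0.058 against 0.063 at f = 10%), so it should not replace the primary.
- Report the number with no ADKS at any visit, split by BHPro registration, for example in the SAP 6 participant flow. If nobody went unregistered, the matter closes there.
- State that percentage of chapters completed is in the imputation model, coded 0 and not missing for non-registrants.

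Cost: a few lines of SAP text and code on data already held, a little more analysis, and possibly a slightly smaller ITT change shown alongside the primary one.

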8.2 Analysis of Primary Outcome

The primary outcome is dementia literacy following participation in the study, as measured by the **Alzheimer's Disease Knowledge Scale (ADKS)**. The ADKS is designed to assess knowledge about Alzheimer's Disease (AD) among laypeople, patients, caregivers, and professionals. This self-report questionnaire contains 30 true/false items. The total score is quantitative and ranges from 0-30, with a higher score indicating better knowledge about AD.

An MMRM will be used to evaluate the primary outcome measure of change over time on the ADKS. This model will examine the effect of time (baseline, 6-month, 12-month), adjusted for baseline characteristics including age, sex, race, cognitive status and education.

Inference on change in ADKS from baseline will be conducted via least squared mean estimates as implemented in the R 'emmeans' package ⁹.

Descriptive statistics will be used to describe measures of user satisfaction, usability and acceptance of BHPro overall and by age, sex, gender, educational level, diagnostic group, and severity of cognitive impairment (MCI vs CU).

8.4 Exploratory Analyses

8.4.1 Change in attitudes toward dementia following participation in the study as measured by **Sections B and D of the Perceptions Regarding Investigational Screening for Memory in Primary Care (PRISM-PC)**.

The **PRISM-PC** questionnaire captures participants' acceptance, perceived harms, and

perceived benefits of dementia screening. Sections B and D will be used to assess attitudes toward dementia and dementia screening. Section B consists of 8-items and measures acceptance of screening. Section D consists of 29 items and measures benefits and harms of dementia screening including 4 constructs (benefits, stigma, suffering, and negative impact of screening on independence). All items are rated on a 5-point scale (strongly agree, agree, I don't know, disagree, strongly disagree). The total score is quantitative and ranges from 36-180. Positive statements were reverse coded so that a total higher score indicates greater acceptance and higher perceived benefit of dementia screening.

An MMRM will be used to evaluate performance over time on the PRISM-PC. This model will examine the effect of time (baseline, 6-month, 12-month) adjusted for baseline characteristics including age, sex, race, cognitive status and education. The MMRM will be fit to the ITT sample (that is, the same multiply imputed dataset described in section 8.1), to the mITT sample, and to the 'completers' sample.

8.4.2 Effect of dose (number of chapters completed in BHPro)

Fall-off in use of the program as time on study increases will be monitored, and Cox regression with time-varying covariates will be used to investigate the extent to which a decrease in engagement with BHPro provides an early warning for risk of study dropout.

The effect of dose will be assessed using regression models with restricted cubic splines to allow for non-linearity in the association of the number of chapters completed within the BHPro program (a measure of dose) and dropout status.

8.4.3 Change in modifiable risk factors following participation in the study, as measured by **BHPro Lifestyle Risk Questionnaires**.

Each lifestyle questionnaires includes a quantitative total score.

Physical Activity: The International Physical Activity Questionnaire-Short Form is a brief 7-item self-report measure that captures types of and intensity of physical activity and sitting time. The total score is calculated by summing the accrued number of points assigned per question. The total score ranges between 0-9, with a higher score indicating more physical activity.

Cognitive Engagement: A 6-item questionnaire assessing types and duration of cognitively engaging activities. The total score is calculated by summing the accrued number of points assigned per question. The total score ranges between 0 and 36, with a higher score indicating more cognitively stimulating activities.

Diet: Shorter 11-item version of the Eating Pattern Self-Assessment Questionnaire developed by CCNA Team 5. The total score is calculated by calculating the accrued number of points assigned per question. The total score ranges between 0 and 22, with a higher score indicating more healthy eating habits.

Sleep: Brief 8-item questionnaire developed by BHPro sleep module content leads that assesses sleep duration, sleep patterns, and difficulties and daytime fatigue over the past 3 months. The total score is calculated by summing the accrued number of points

assigned per question. The total score ranges between 1 and 16, with a higher score indicating healthier sleep.

Social & Psychological Health: An 8-item questionnaire comprising 1 item on loneliness, 1 item on ageism, 1 item on subjective age, 1 item on essentialist beliefs of aging and 4 items on depression, anxiety, stress, and social support from STOP-D. The total score is calculated by summing the accrued number of points assigned per question. If a user selects '0/Never' for example, they receive 0 points for that question. The total score ranges between -1 and 50, with a higher score indicating poorer social and psychological health (a lower score indicates better health).

Vascular Health: 12-item self-report questionnaire developed by the BHPro Vascular Health team based on the American Heart Association's Life's Simple Seven checklist of the main risk factors for heart disease and stroke. The total score is calculated by summing the accrued number of points assigned per question. The total score ranges between -4 and 8, with a higher score indicating better vascular health.

Vision & Hearing: 10-item questionnaire developed by BHSP Vision and Hearing Module content leads that assesses perceived visual and auditory ability and actions taken to address potential vision/hearing difficulties. The total score is calculated by summing the accrued number of points assigned per question. If a user selects "Yes" for example, they receive 2 points for that question. The total score ranges between 0 and 20 points, with a higher score indicating poorer vision and hearing (a lower score indicates better health). Response: higher scores = more functional impairment as a proxy for risk.

An MMRM will be used to evaluate performance over time on the BHPro Lifestyle Risk Questionnaires. This model will examine the effect of time (baseline, 6-month, 12-month) adjusted for baseline characteristics including age, sex, race, cognitive status and education. The MMRM will be fit to the ITT sample (that is, the same multiply imputed dataset described in section 8.1), to the mITT sample, and to the 'completers' sample.

8.4.4 Cognition

8.4.4.1 Change in **global cognition** will be assessed using a composite outcome score computed from the following measures from Neuropsychological Test Battery:

- Craft Story – Immediate Recall – Total Story Units Recalled - Verbatim
- Craft Story – Delayed Recall – Total Story Units Recalled - Verbatim
- ADAS-COG Word Recall – Total Immediate Recall (trial 1 + trial 2 + trial 3)
- ADAS-COG Word Recall – Delay (total correct)
- Brief Visuospatial Memory Test-Revised (BVMT-R)- Total Recall (trial 1 + trial 2 + trial 3)
- BVMT-R Delayed Recall
- Oral Symbol Digit Modalities Test – Total Raw Score
- Oral Trail Making Test (Part A) – Time To Completion
- Oral Trail Making Test (Part B-A)
- DKEFS Category Fluency – Total Correct (animals only)
- DKEFS Color-Word Interference Test (CWIT) – Condition 2 Word Reading – Time to Complete

- DKEFS CWIT – (Condition 3 Inhibition-Condition 2 Word Reading)

Z-scores for each participant on each measure will be calculated using the overall mean and SD of all participants at baseline as reference. Scores from each individual test will be converted to z-scores that typically range from -3 to 3, with higher scores reflecting better performance, and averaged to form a composite. For purposes of this analysis, the z scores for the timed tasks (Oral Trail Making Test (Part A and Part B) and Color-Word Interference Test (Word Reading and Inhibition)) are reverse coded. If more than 25% of the component measures are missing, the global cognitive composite score will be missing.

An MMRM will be used to evaluate change in the global cognitive outcome from baseline to Month 12, adjusted for baseline characteristics including age, sex, race, cognitive status and education. The MMRM will be fit to the ITT sample (that is, the same multiply imputed dataset described in section 8.1), to the mITT sample, and to the 'completers' sample. Inference on the change will be conducted through least-square means estimates.

Additional exploratory analysis will be conducted by analyzing the data obtained by first calculating the domain-specific outcomes (see section 8.4.4.2 below), and then aggregating the domain-specific outcomes to calculate the global cognitive outcome score. Methods similar to the above will be used for the analysis.

8.4.4.2 Change in the subdomains of memory, processing speed, and executive functions will be assessed using domain-specific composites.

The memory subdomain is comprised of the following tests:

- Craft Story – Immediate Recall – Total Story Units Recalled - Verbatim
- Craft Story – Delayed Recall – Total Story Units Recalled - Verbatim
- ADAS-COG Word Recall – Total Immediate Recall (trial 1 + trial 2 + trial 3)
- ADAS-COG Word Recall – Delay (total correct)
- BVMT-R Total Recall (trial 1 + trial 2 + trial 3)
- BVMT-R Delayed Recall

The processing speed subdomain is comprised of the following tests:

- Oral SDMT – Total Raw Score
- Oral TMT (Part A) – Time To Completion
- DKEFS CWIT – Condition 1 Color Naming – Time to Complete

The Executive Functions subdomain is comprised of the following tests:

- Oral Trail Making Test (Part B – Part A)
- DKEFS Category Fluency – Total Correct (animals only)
- DKEFS CWIT- (Condition 3 Inhibition- Condition 2 Word Reading)

Z-scores for each participant on each measure will be calculated using the overall mean and SD of all participants at baseline as reference.

To calculate each domain-specific cognitive composite, scores from each individual test within the subdomain will be converted to z-scores that typically

range from -3 to 3, with higher scores reflecting better performance, and averaged to form a composite. For purposes of this analysis, the z scores for the timed tasks (Oral Trail Making Test (Part A and Part B) and Color-Word Interference Test (Word Reading and Inhibition)) are reverse coded. Composite scores are computed when 50% or more of the component test scores are available.

An MMRM will be used to evaluate change from baseline to Month 12 in each of the domain-specific composites z-scores, adjusted for baseline characteristics including age, sex, race, cognitive status and education. The MMRM will be fit to the ITT sample (that is, the same multiply imputed dataset described in section 8.1), to the mITT sample, and to the 'completers' sample. The change will be estimated using the least-square mean contrast.

8.4.4.3 Change in performance based on “**Burst**” Cognitive Testing (**MyCogHealth Mobile App**) that addresses: 1) Within-person change in asymptote, daily variation and within-burst practice effects of “burst” cognitive testing; 2) Between- and within-person factors including self-rated emotional reactivity and its association with variation in cognitive performance over the BHPro intervention

Mixed effects modelling for burst cognitive testing will be used to disambiguate sources of performance variance within-day, across days, and across burst-to-burst timescales and to include within-person factors (i.e., stress, mood) that influence variation in performance. The data will be evaluated within-person cognitive change, cognitive variation, and differential retest/learning effects at the individual level as potential digital biomarkers.

We will investigate the association of participant demographic characteristics, cognitive status, and BHPro compliance with performance and change in MyCogHealth performance parameters. Exploratory analyses will examine concordance between the MyCogHealth outcome measures and the NTB, Cogniciti BHA, and BHPro Lifestyle Risk factors.

8.4.4.4 Change in performance based on online self-administered cognitive testing with the **Cogniciti Brain Health Assessment (BHA)**.

To evaluate the feasibility of online cognitive assessment, we will examine the number of completed self-administered assessments using the Cogniciti BHA at Baseline, Month 6, and Month 12. We will examine the association of participant demographic characteristics, clinical diagnosis, and BHPro compliance with performance and change from baseline on the Overall Brain Health Assessment Score and each of the subtests of the Cogniciti BHA.

The primary outcome measure for the Cogniciti BHA is the Overall Brain Health Assessment Score. One representative score is calculated from each of the four BHA subtests, and an overall score is calculated from these subtest scores.

1. Spatial Working Memory: Number of responses. This score is the number of

responses (i.e., the number of clicks) required to find all six pairs of shapes, summed across the three trials.

2. Face-Name Association: Recognition accuracy. This is an overall accuracy score for the 24 test items, expressed as a percent. It is calculated as the number of correct hits (i.e., “yes” responses to intact pairs) plus the number of correct rejections (i.e., “no” responses to recombined pairs) divided by the total number of items.

3. Stroop Interference: Incongruent reaction time. The score on this test is the median reaction time, expressed in milliseconds, on the incongruent trials. Of the 30 incongruent trials, reaction times were included only for those trials on which the correct response was given.

4. Letter-Number Alternation: Time to completion. This score is the total time required to complete the alternating letter-number sequence, expressed in seconds.

5. Overall BHA Score. Each of the 4 subtest scores are converted to z-scores based on normative data from Troyer et al 2014¹⁰. The overall score is calculated as the mean of the four z- scores and is converted to a percentile to aid interpretation.

Exploratory analyses will also examine concordance between the Cogniciti BHA outcome measures and examiner-administered neuropsychological assessments.

8.4.4.5 Change in modifiable risk factors and relationship to change in cognition.

Multivariate mixed linear regression models will be used to investigate the dynamic relationship between baseline level and longitudinal change in health behaviours (as assessed by the lifestyle risk questionnaires) and performance on the Cogniciti BHA and MyCogHealth cognitive tasks. For those models that investigate change in performance on MyCogHealth, session-level ratings of participant mood, sleep quality, and exercise will be investigated as mediators of the association between changes in health behaviours and cognition. All analyses will be adjusted to age, sex, and education. Regression models will be fit to the ITT sample (that is, the same multiply imputed dataset described in section 8.1), to the mITT sample, and to the ‘completers’ sample. A sensitivity analysis will stratify the cohort by cognitive status.

